PROTOCOL

Obturator Nerve Block and Pericapsular Nerve Group Block for Preventing Obturator Nerve Reflex: A Randomized Controlled Trial

May 24, 2024

Block and Pericapsular Nerve Group Block for Preventing Obturator Nerve Reflex: A Randomized Controlled Trial

1 Research background Bladder cancer is a common urological tumor in clinical practice. Transurethral resection of bladder tumor (TURBT) is a widely used surgical treatment for bladder cancer, offering advantages such as minimal invasiveness and high patient acceptance.

TURBT is commonly performed under spinal anesthesia. The obturator nerve is located near the inferolateral wall of the bladder and the bladder neck within the pelvis. During transurethral resection of tumors in these areas, the electrical current can easily pass through the bladder wall, directly stimulating the obturator nerve, leading to an obturator nerve reflex in the patient.

It has been reported that during TURBT involving the lateral bladder wall without ONB, 40% of patients experienced sudden thigh movement, and 5.7% had bladder perforation. A retrospective study compared the recurrence rates of patients with lateral bladder wall tumors undergoing TURBT with or without ONB, showing that ONB prolonged the average time to bladder tumor recurrence by 7.8 months and 15 months, respectively.

The obturator nerve originates from the anterior branches of the second, third, and fourth lumbar nerves. It runs along the lateral wall of the lesser pelvis and, after passing through the obturator canal, immediately courses between the pecten muscle and the external obturator muscle, extending to the anterior thigh. The obturator nerve divides into anterior and posterior branches during its course. In cadaveric studies, the bifurcation of these two major branches was identified as occurring within the pelvis (23.22%), within the obturator canal (51.78%), or in the medial thigh (25%).

The nerve passes through the obturator foramen into the thigh, where it divides into anterior and posterior branches. After exiting the obturator foramen, it extends deeper into the pecten muscle. Typically, the anterior branch runs along the fascial plane between the adductor longus and adductor brevis, while the posterior branch runs between the adductor brevis and adductor magnus.

The pericapsular nerve group (PENG) block is a novel ultrasound-guided nerve block technique. By injecting local anesthetic between the psoas major muscle and the pubic bone, it provides analgesia for patients with hip fractures.

The obturator nerve (ON) and accessory obturator nerve (AON) run between the pectenous muscle and the external obturator muscle. Injecting local anesthetic between the pectenous muscle and the superior pubic ramus can theoretically block both the obturator nerve and the accessory obturator nerve through diffusion.

In a 2022 study, researchers simulated a PENG block by injecting 20 mL of methylene blue into 18 hip joint specimens. The cadavers were then dissected to document the presence and dye staining of the femoral, lateral femoral cutaneous, obturator, and accessory obturator nerves, as well as the articular branches of the femoral, obturator, and accessory obturator nerves. The results indicated that the PENG block can successfully block the main trunk of the obturator nerve.

The primary reason for obturator nerve blockade may be that the iliopubic fascia forms the medial end of the iliac fascia, acting as a barrier to prevent the local anesthetic from further medial spread to reach the obturator nerve within the deep pectenous muscle. However, the iliopubic fascia has a relatively short course in the cranio-caudal direction, suggesting that using a high volume of local anesthetic with a PENG block could potentially result in obturator nerve blockade below the pubis.

Directory of references

2.1 Study Purpose

2.1.1 Main study objective:

Evaluate the effectiveness of the pericapsular nerve group (PENG) block in preventing obturator nerve reflex during transurethral resection of bladder tumors.

2.1.2 Secondary study objective:

Evaluate the safety of the pericapsular nerve group (PENG) block in preventing obturator nerve reflex during transurethral resection of bladder tumors.

2.2 Study endpoint

2.2.1 Primary study endpoints

Percentage reduction in adductor muscle strength at 5, 10, 15, 20, 25, 30 minutes, and 3 hours post-administration.

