2.2.2.2. Safety study endpoint

1) Incidence of adverse reactions such as local anesthetic toxicity and nerve injury post-administration.

2) Procedure time and number of needle passes.

3. Expected results

Pericapsular nerve group (PENG) block is effective and safe in preventing obturator nerve reflex during transurethral resection of bladder tumors.

4. Design and method of the study

This clinical study uses a single-center, randomized, single-blind, parallel controlled trial design, divided into screening period, treatment period and follow-up periods.

4.1.1 Screening period:

Patients undergoing transurethral resection of bladder tumors signed informed consent forms for enrollment. Subjects who met all inclusion criteria and did not meet any exclusion criteria were randomized in a 1:1 ratio to the experimental and control groups, either one day before surgery or on the day of surgery.

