10.2 Responsibility of the project leader

The project leader takes all reasonable steps and provides sufficient resources to ensure the implementation of the research, mainly involving the following aspects:

- A) Ensure that the study complies with relevant national and local regulations, including ethical requirements, patient data protection regulations, etc.
- B) Ensure the effectiveness of quality control and analysis of research results.

11. Results sharing

The intellectual property rights, trial data and research results related to this anatomical study are jointly owned by the Nanjing First Hospital and the Department of Anesthesiology, and the University and the Anatomy Teaching and Research Section of Nanjing Medical University.

The intellectual property rights, trial data and research results related to this clinical study are owned by Nanjing First Hospital and the Department of Anesthesiology.

12. Data analysis

Data collection: It was collected by the same anesthesiologist who did not know the grouping situation.

Statistical analysis was performed using SPSS 22.0 software. Measurement data were expressed as mean \pm standard deviation ($X \pm s$), and comparisons between groups were conducted using the paired t-test. Categorical data were compared using the chi-square (χ^2) test, and ordinal data were compared using the rank-sum test. A

P-value of <0.05 was considered statistically significant.

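### Seven time points are all primary, none is singled out, and each may be tested at P<0.05: if any one suffices, the false-positive risk is about 11% to 23% at assumed correlations of 0.9 to 0.5

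*Protocol*

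**What the plan says.** Protocol section 2.2.1, headed "2.2.1 Primary study endpoints", contains one entry: "Percentage reduction in adductor muscle strength at 5, 10, 15, 20, 25, 30 minutes, and 3 hours post-administration". Six readings fall in the first half hour and the seventh at 3 h. None is ranked above the others and no summary across them is defined.

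Protocol section 12 is the only analysis text. For measurement data it states that "comparisons between groups were conducted using the paired t-test", and its single criterion is that a "P-value of <0.05 was considered statistically significant". It mentions no multiplicity adjustment, ordering of tests or repeated-measures model.

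Protocol section 3 gives the expected result, "Pericapsular nerve group (PENG) block is effective and safe in preventing obturator nerve reflex", without tying it to any time. Section 4.1.1 describes two parallel groups, "randomized in a 1:1 ratio to the experimental and control groups".

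**The concern.** The protocol fixes what is primary and the significance threshold, but not how seven primary readings become one answer. Two things are at stake.

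- **Type I error.** If a significant result at any one time may be reported as a primary difference, there are seven chances to find one by luck, and the overall risk exceeds 5%.
- **Interpretation.** If the groups differ at some times and not at others, the protocol does not say which result answers the primary question. The readings run from 5 minutes to 3 hours, so a mixed pattern is easy to imagine. The time to emphasise could then be chosen after seeing the data.

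**Working it through.** The protocol states no family-wise error rate, power or sample size, so it has no figure of its own to reproduce. None of these is needed for the calculation.

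**Inputs**

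- Number of primary comparisons: k = 7 (section 2.2.1).
- Threshold per test: 0.05 (section 12). Sidedness is not stated; two-sided is assumed, so c = 1.96.
- Correlation ρ between times: not in the protocol. Assumed, and varied.
- Each test is assumed to have its nominal 5% size, and there is no true difference at any time.

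**Independence limit** (implausible for repeated readings on one patient): 1 − 0.95^7 = 0.302, or 30.2%.

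**Equal correlation ρ between all pairs of times.** Write each test statistic as Z_i = √ρ·U + √(1−ρ)·E_i, with U and the E_i independent standard normal. The chance of at least one significant result is

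1 − ∫ φ(u)·[Φ((c − √ρ·u)/√(1−ρ)) − Φ((−c − √ρ·u)/√(1−ρ))]^7 du.

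For one direction only, the second Φ term is dropped. Numerical integration gives:

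| Common ρ | Any time, either direction | Any time, favouring one named group (nominal 2.5%) |
|---|---|---|
| 0.5 | 23.0% | 11.5% |
| 0.7 | 17.8% | 8.9% |
| 0.8 | 14.9% | 7.4% |
| 0.9 | 11.4% | 5.7% |
| 0.95 | 9.2% | 4.6% |
| 0.99 | 6.7% | 3.4% |

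**Check on the normal approximation.** Simulated two-sample t-tests with assumed sizes of 20, 30 and 50 per group give 22.8% to 23.4% at ρ = 0.5 and 11.2% to 11.5% at ρ = 0.9, in agreement with the table.

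**Other correlation patterns (simulation, either direction)**

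- Six early readings correlated 0.9 with each other and 0.5 with the 3 h reading: 14.2%.
- Correlation decaying with lag in equal steps (AR(1)): 14.7% at an adjacent correlation of 0.9, 22.5% at 0.7 and 26.7% at 0.5.

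**The opposite rule.** If all seven had to be significant, the chance under no difference anywhere is 0.04%, 0.26% and 1.4% at ρ = 0.5, 0.7 and 0.9. There is no inflation.

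**If all seven stay primary with an adjustment.** The per-test level is 0.05/7 = 0.0071, with critical value 2.690. The family-wise error is then 4.0%, 3.2% and 2.0% at ρ = 0.5, 0.7 and 0.9. The cost in power per time:

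- 80% power at 0.05 becomes Φ(1.960 + 0.842 − 2.690) = Φ(0.112) = 54%. Restoring it takes (2.690 + 0.842)²/(1.960 + 0.842)² = 1.59 times the patients.
- 90% power at 0.05 becomes Φ(1.960 + 1.282 − 2.690) = Φ(0.552) = 71%. Restoring it takes (2.690 + 1.282)²/(1.960 + 1.282)² = 1.50 times the patients.

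**The case against.** The strongest reply is that much of this is absence. Multiplicity handling and the success rule are often left to a statistical analysis plan, which may exist. Section 12 is one generic paragraph that never mentions the seven times. A t-test can also be run on a per-patient summary, so section 12 does not force seven tests, and section 2.2.1 can be read as one variable followed over time.

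Part of this stands. Seven separate tests are what the two sections allow, not a plan they spell out, and *unadjusted* means only that the protocol contains no adjustment. But what counts as primary is a protocol matter. Section 2.2.1 settles it by making all seven times primary, with neither a leading time nor a summary. A later plan that picked one would be changing that definition, so the text needs correcting in any case.

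Three further points concern the numbers.

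- The either-direction figures include false differences favouring the obturator nerve block, which would not support section 3's expectation about the PENG block. This is fair, and the one-direction figures belong beside them. They still exceed the nominal 2.5%.
- The 11% to 23% range is not a bound. This is correct: it assumes equal correlation between all pairs. Correlation decaying with lag gives about 15% to 27%, and near-perfect correlation gives less.
- The paired test named in section 12 does not fit two independent groups, so the calculation assumes a test of correct size. This is true, but it is a separate issue that does not affect the point made here.

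**Conclusion.** The concern holds. The protocol makes seven readings primary, sets one unadjusted threshold and does not say which result, or how many, decides the primary question. Claiming a primary difference from any single time is therefore consistent with the text.

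Under that any-one-time rule, with two-sided tests of nominal size, the chance of at least one false difference is about 11% to 23% for common correlations of 0.9 to 0.5. These are illustrations resting on assumed correlations. The risk exceeds 5% in every pattern examined, including a correlation of 0.99. The lack of a stated rule is a defect whatever the correlation. It should be fixed, and a wording change is enough to do so.

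**What to change.** In section 2.2.1, before any outcome data are seen, do one of the following and give the reason.

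1. **Name one of the seven times as primary.**
2. **Name one summary contrast as primary**, for example the between-group difference in each patient's mean percentage reduction over the listed times. An unweighted mean gives six of its seven weights to the first 30 minutes and one to 3 h, so the weighting should be deliberate.

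These are different estimands and the protocol does not favour either, so the choice belongs to the investigators. Test the chosen one at two-sided 0.05. Make the remaining times secondary and report them as between-group estimates with 95% confidence intervals.

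3. **If all seven stay primary**, state in section 12 that Holm (or a fixed level of 0.0071) is applied and that a difference is claimed only at times that pass it.

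The cost is text in sections 2.2.1 and 12, with no new measurements. Under options 1 and 2, a difference at a single non-primary time can no longer be presented as the primary result. Under option 3 with the fixed level, power per time falls from 80% to about 54%, or from 90% to about 71%, unless the sample is about 1.59 or 1.50 times as large. Holm loses no more than that.

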2.2.2 Secondary study endpoints

2.2.2.1 Effectiveness study endpoint

1) Presence of obturator nerve reflex during surgery.

2) Duration of the surgery

3) Surgeon satisfaction and patient satisfaction.

2.2.2.2. Safety study endpoint

1) Incidence of adverse reactions such as local anesthetic toxicity and nerve injury post-administration.

2) Procedure time and number of needle passes.

3. Expected results

Pericapsular nerve group (PENG) block is effective and safe in preventing obturator nerve reflex during transurethral resection of bladder tumors.

4. Design and method of the study

This clinical study uses a single-center, randomized, single-blind, parallel controlled trial design, divided into screening period, treatment period and follow-up periods.

4.1.1 Screening period:

Patients undergoing transurethral resection of bladder tumors signed informed consent forms for enrollment. Subjects who met all inclusion criteria and did not meet any exclusion criteria were randomized in a 1:1 ratio to the experimental and control groups, either one day before surgery or on the day of surgery.

4.1.2 Treatment Period

Upon entering the operating room, HR, BP, ECG, and SpO₂ were monitored. Intravenous access was established, and oxygen was administered. Patients were randomly divided into two groups using a random number table: the pericapsular nerve group (PENG) block group (P group) and the obturator nerve block group (O group).

In the P group, patients were placed in the supine position, and the inguinal region was exposed, followed by routine disinfection and draping. A convex ultrasound probe (frequency 2-5 MHz) was positioned at the patient's inguinal ligament, with one end directed toward the anterior inferior iliac spine (AIIS), clearly visualizing the bony prominences of the iliopubic eminence and the AIIS. An out-of-plane technique was used, with the needle tip directed medially toward the pectenous muscle. Care was taken to avoid the femoral artery, vein, and nerve during needle insertion. Once the

needle tip reached the space between the pectineus muscle and the pubic bone, and after confirming no blood upon aspiration, 30 ml of 0.375% ropivacaine was injected. In the O group, patients were placed in the supine position, with the affected thigh abducted and externally rotated. The ultrasound probe was positioned at the inguinal ligament and moved medially to locate the adductor muscles and pectineus muscle. Care was taken to avoid the femoral artery and vein, and the obturator nerve and fascial planes of the muscle layers were identified step by step. The needle was inserted parallel to the long axis of the probe. After confirming no blood upon aspiration, 15 ml of 0.375% ropivacaine was injected into the fascial plane between the adductor brevis and adductor magnus, as well as into the midportion of the adductor longus and adductor brevis muscles.

Anesthesia induction was performed with propofol at 1-2 mg/kg, sufentanil 10 µg, and remifentanil 1.5 µg/kg, followed by mask ventilation for 5 minutes. A laryngeal mask was inserted for mechanical ventilation. The ventilation mode selected was pressure-controlled with volume guaranteed, with FiO₂ at 45%, tidal volume (VT) 6-8 ml/kg, PEEP 4-6 cmH₂O, Iratio 1:2, and respiratory rate (RR) 12-20 breaths per minute. Anesthesia maintenance was achieved with a continuous infusion of propofol at 4-6 mg/kg/h and remifentanil at 0.1–0.3 µg/kg/min.

4.1.3 Follow-up period

Neurological complications, hematoma at the puncture site, patient satisfaction, and doctor satisfaction.

5.0 Study the implementation process

After entering the room, intravenous access was established, and routine monitoring of ECG, NBP, and SpO₂ was performed. Based on group assignment, the same physician experienced in nerve blocks performed either the obturator nerve block or the pericapsular nerve group (PENG) block. Anesthesia was induced and maintained according to a standardized protocol. The same anesthesiologist, who was unaware of the group assignments, collected various study parameters and data.

6. Subject recruitment and protective measures

6.1 Inclusion criteria

Aged 18 years or older: scheduled for TURBT for unilateral bladder tumor: able to understand and provide informed consent.

6.2 Exclusion criteria

Patients who refuse or are unable to provide informed consent; allergic to local anesthetics, insensitive to propofol or general anesthetics; pregnant women; severe liver dysfunction; evidence of infection at or near the proposed puncture site; any sensory or motor impairment of the lower limbs; recent (within 6 months) lower limb joint replacement surgery.

6.3 Exit criteria

Patients may withdraw their informed consent and withdraw from the trial at any time.

The investigator may decide on the subject to terminate the withdrawal from the study in the following circumstances

- 1) Any medical condition occurring in the study may lead to the risk of continuing the study subjects;
- 2) Unable to complete the trial according to the protocol for various reasons;
- 3) The researcher judges other situations that should withdraw from the trial.

7 Informed consent

7.1 The Informed Consent Form

The informed consent was in accordance with the ethical principles outlined in the Declaration of Helsinki. The informed consent form detailed the study protocol and process, and fully explained the risks of the study.

The informed consent form also states that the records of the individual identity must be kept confidential, but the research team and regulators can access the subject information.

7.2 Informed consent process and recording

Informed consent begins before the individual consent to participate in clinical studies and continued throughout the course of the clinical study.

7.3 Confidential

Personal patient information will be given as confidential information. All patient data obtained from the patient cases will be kept as confidential. Patients will be identified by their name acronym and the numbers provided at the time of study inclusion. Patients or their families will be aware of the anonymity of the data and their right to protect their privacy. However, it is also important to understand the fact that the data will be submitted to the subject responsible unit or the government management authority, and may also be submitted to institutions such as the Ministry of Health for inspection and evaluation. The participating physician will keep a list of patient personal data (patient data and corresponding patient names) for confirmation of the record.

8. Quality control and quality assurance

8.1 Qualification of research unit and researcher qualification

The research unit shall have the experience in drug research, the facilities and conditions of the department where the project belongs shall meet the needs of safe and effective clinical research, and the researchers shall have the professional expertise, qualifications and ability to undertake the clinical research, and shall be trained in GCP regulations.

8.2 Training of the researchers

Before the start of the study, the research leaders of each center should organize the researchers to study the program, and only the researchers who have passed the program training can participate in the study to ensure that the researchers have a consistent understanding of the protocol. For important assessment scales, relevant personnel in the participating centers need systematic training and even obtain corresponding qualification certificates.

8.3 Surveillance of clinical trials

A hospital ethics committee and institutional review board may conduct a systematic review of the clinical trial-related activities and documents, to evaluate whether the trial was conducted in accordance with the trial protocol, SOP, and relevant

regulations, and whether the trial data are timely, true, accurate, and complete records. The audit should be performed by those who do not directly involve the clinical trial.

9. Organization and management of the research

9.1 Change of the scheme

All additional or referenced appendices are integral parts of the scheme. No one shall make any modifications or revisions to any part of the research protocol, as signed by the investigator and the principal of the project, unless these changes or revisions have been fully discussed. And through the unanimous consent of the researcher and the subject leader. Any agreed modification will be recorded and will be signed by the investigator and the project leader

The case is filed together.

9.2 Retention of the records

The investigator shall keep all the detailed original documents of the subject, and record the trial process, medication status, laboratory examination data, safety data and efficacy assessment in the case report form. The recorded data shall be complete, timely and clear. The original documents and medical records should be clear, detailed and easily identified by those participating in this clinical trial. The case report form and the original files can only be modified by the investigator. No modification to the case report form and the original file shall smear the original data off. The correct way to modify is to line the original data, and then write the modified data next to the original data, and sign the date and the name of the modification. Test data shall be retained until 5 years after the termination of the test.

